10.9.7 Safety Monitoring

The choice of sedative drugs, dose, and route of administration will be based on clinical indications as judged by the Attending Physician and will not be changed for the purposes of the study. The BIS™ monitor will not be used in situations where the placement of the probe will interfere with a procedure, cause scan artifacts, or where the presence of a metal monitor is contraindicated (e.g., MRI scans). Therefore, we believe there is only a minimal increase in risks from participating in the study. This risk relates to the possibility of developing irritation to the skin at the site of sensor placement.

Subjects will be monitored for Adverse Events, Unanticipated Adverse Device Effects, Serious Adverse Events, and Device-Related Adverse Events from BIS™ sensor applications through the BIS™ sensor removal.

Any study procedures may be discontinued for the subject's safety. For patient safety, modifications to the procedure steps will be left to the judgment of the Principal Investigator.

10.10 Assessment of Efficacy

Refer to Section 14.

10.11 Assessment of Safety

For safety analyses, adverse events will be summarized using frequency counts and percentages, refer to *Section 14*. Descriptive statistics will be provided by event type, severity, and relationship to study procedures and devices. Individual listings of adverse events, including event type, start date, duration, severity, and device-relatedness, will be provided as appropriate. Adverse events occurring during the procedure or 48 hours after the procedure will be recorded. For AEs and AE reporting requirements, refer to *Section 12*.

10.12 Recording Data

The study will utilize the electronic Case Report Forms (eCRFs) in a database provided by the Sponsor.

Medtronic Business Restricted

eCRF completion may be delegated by the Principal Investigator (documented on the Delegated Task List) to other study personnel, but the Principal Investigator remains responsible for the accuracy and integrity of all data entered in eCRFs. The Principal Investigator or delegated Sub-Investigator is required to approve all data on eCRFs via electronic signature.

Additional details regarding procedures used for data review, database cleaning, issuing and resolving data queries, and identification of steps for creation, modification, maintenance, archiving retrieval or transmission of source data via any computerized systems will be provided in the study-specific Data Management Plan (DMP).

10.13 Deviation Handling

The Investigator is required to conduct this study in accordance with the protocol, Good Clinical Practice (GCP), Institutional Review Board (IRB) requirements, and applicable regulations. The Investigator is not allowed to deviate from the above-mentioned documents except under emergency circumstances to protect the rights, safety, and well-being of human subjects.

A study deviation is defined as an event when the investigator or site personnel did not conduct the study according to the protocol or the clinical trial agreement.

The Investigator is required to obtain prior approval from the sponsor and IRB *before* initiating deviations from the Clinical Investigation Plan, except where necessary to protect the life or safety and physical well-being of a subject in an emergency. Such approval will be documented in writing and maintained in the study investigator files.

Major deviations are defined as deviations with respect to:

- Patient informed consent procedure;
- Patient eligibility criteria;
- Late reporting of Serious Adverse Event /Serious Adverse Device Effect /Unanticipated Adverse Device Effect (for reporting refer to Section12).

Deviations will be recorded at the site and reported to Medtronic on the eCRF and via email to the study manager. The Protocol Deviation eCRF document shall be signed and dated by the Investigator or his authorized designee. At a minimum, the following information will be recorded:

- identification of the Investigator and site
- description of deviation
- date of occurrence
- reason for the deviation

Medtronic Business Restricted

- patient identifier, if associated with the event

Deviations will be entered into a database to allow a comprehensive review on a regular basis for identifying trends that warrant additional preventive or corrective actions to mitigate further occurrence. Clinical study management at Medtronic shall conduct this review. Repetitive or serious investigator compliance issues may result in the need to initiate a corrective action plan, and in some cases, freeze enrollment or ultimately terminate the Investigator's participation in the clinical study.

Study deviations must be reported to Medtronic, regardless of whether medically justifiable, pre-approved by the study leader (see contact details section) or taken to protect the subject in an emergency.

In the case that the deviation involves a failure to obtain a subject's informed consent or is made to protect the life or physical well-being of a subject in an emergency, the deviation must be reported to the IRB as well as the study leader as soon as possible after the occurrence of the event. Reporting of all other study deviations should comply with IRB policies and/or local laws.

The Investigator shall adhere to IRB requirements and procedures for reporting study deviations.

All deviations from the CIP shall be included in the final report.

10.14 Subject Exit, Withdrawal or Discontinuation

The subject's parent and/or legal guardian or the subject has the right to withdraw from the study at any time and for any reason without sanction, penalty or loss of benefits to which the subject is otherwise entitled, and without jeopardizing their future medical care. The Investigator may withdraw the subject at any time to protect the health, safety, or welfare of the subject. Every effort should be made to collect the status of any ongoing adverse events, at a minimum.

If the subject discontinues participating in the study before completing the study requirements, the reason for withdrawal will be recorded in the subject's study records and eCRF.

If withdrawal from the study is due to problems related to the investigational device safety or performance, the Investigator shall ask for the subject's permission to follow his/her status outside the clinical study.

- When and how to withdraw subjects from the study product treatment
- The type and timing of the data to be collected for withdrawn subjects
- Whether and how subjects are to be replaced
- The follow-up for withdrawn subjects.

There are many scenarios in which a subject may exit the study. The following terms are used for withdrawal and completion:

Medtronic Business Restricted

- Screen Failure: Subject did not meet the study inclusion/exclusion criteria;
- Study Withdrawal: Removal from the study after enrollment by either subject /legal guardian, PI, or Sponsor, or technical problems;
- Study Complete: Completion of all study related activity by the subject;
- Other: protocol deviation leads to replacement of subject

10.14.1 Study Exit

A study exit eCRF is required for all subjects. Prior to exiting a subject from the study, it is recommended to follow the subject until all ongoing system and/or procedure related AEs are resolved or unresolved with no further actions planned. Following exit, subjects will continue to receive standard medical care. Upon exiting from the study, no further study data will be collected, or study visits will occur for the subject. All data available through the time of the subject's exit will be used for analysis.

Subjects are urged to remain in the study as long as possible but may be exited from the study for any of the following situations:

- Study completed
- Subject did not meet inclusion/exclusion criteria
- Subject did not provide consent or data use protection authorization
- Subject chooses to withdraw (e.g., consent withdrawal, relocation to another geographic location)
- Investigator deems withdrawal necessary (e.g., medically justified, inclusion/exclusion criteria not met, failure of subject to maintain adequate study compliance)

The following information is required to be collected at study exit:

- Reason for exit

If discontinuation is because of safety, the subject shall be asked to be followed for collecting safety data outside the clinical investigation.

10.14.2 Subject Chooses to Exit (i.e. Revokes Consent)

A subject can withdraw from the study at any time. If the subject wishes to exit from the study (i.e. the subject revokes consent), the study site is required to document the reason for exit on the Exit CRF. In addition, study sites shall follow the regulations set forth by the governing IRB. If possible, the following data should be collected prior to subject withdrawal:

- Reason for exit

10.14.3 Investigator Withdraws Subject

No subjects should be withdrawn by investigators unless compelling medical justification is present. It is recommended investigators discuss any withdrawals with the study team prior to withdrawing subjects. If the subject was randomized, it is preferred to keep the subject in the study and perform study procedures/collect data to the extent possible. If an Investigator Withdrawal is necessary, the following data should be collected prior to subject withdrawal if possible:

- Reason for subject withdrawal

11. Risks and Benefits

11.1. Potential Risks

Risks to participation are primarily physical. There are no social, economic, legal, long-term psychological, or other risks that have been identified. Risks under this protocol relate to both study devices and study procedures. We believe that the risks from the device(s) are in keeping with the definition of non-significant risk devices (NSR). Further, the devices in this study are non-invasive, and the clinical protocol design is minimal risk to the subject. No treatment or treatment decisions will be made during the course of this study. Following is a list detailing potential risks from study devices and the clinical protocol.

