For the BIS™ group, sevoflurane will be titrated to achieve a target BIS™ value of 45 – 60 during maintenance of anesthesia and a target BIS™ value of 60 – 75 beginning at the start of skin closure. In order to protect against inadequate or excessive anesthesia in the BIS™ guided group, the subject will be assessed approximately every 5 minutes for signs of anesthesia. In the event of hypertension and/or tachycardia (>20% above baseline) unexplained by surgical manipulation and or signs of autonomic or somatic responses (e.g., diaphoresis, movement) an additional dose of opioid will be administered. If that does not resolve the situation, then the anesthesiologist may alter the anesthetic concentration outside the BIS™ guidelines to assure adequate anesthesia. In the event of hypotension and/or bradycardia (>20% below baseline), fluids and/or vasopressor will be administered. If that does not resolve the situation, then the anesthesiologist may alter the anesthetic concentration outside the BIS™ guidelines. Subjects with BIS™ values that are outside of the specified range of 45 – 60 during maintenance of anesthesia for >35% of the maintenance duration will be considered a protocol deviation and the subject will be excluded from the final data analysis. The subject will be replaced by an additional enrolled subject. The excluded subject will continue to be monitored for any safety events and the clinician will ensure medical care is provided for any safety event that occurs. Data from excluded subjects will be acknowledged in the final study report but will not be included in the primary statistical analysis. The exception to this exclusion is any data that is outside of the specified range of 45 – 60 as a result of the anesthesiologist titrating sevoflurane as a result of clinical signs or cardiovascular changes defined above. The end-tidal sevoflurane concentration will be continuously recorded. Fentanyl or morphine will be administered at the discretion of the anesthesiologist, for example, 1.5 mcg/kg at induction and 0.75 mcg/kg every 30 minutes in accordance with usual clinical indications.

For the SP group, sevoflurane, fentanyl, propofol, and morphine will be administered at the discretion of the anesthesiologist for example, fentanyl and morphine at 1.5 mcg/kg at induction and 0.75 mcg/kg every 30 minutes in accordance with usual clinical indications.

Medtronic Business Restricted

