Safety Assessments	
This is a prospective, randomized, controlled study where the only change in routine management is the placement of the BIS™ monitor probe on the forehead. The choice of sedative drugs, dose, and route of administration will be based on clinical indications as judged by the attending Anesthesiologist, and it will not be changed for the study.
 
The BIS™ monitor will not be used in situations where the placement of the probe will interfere with a procedure, cause scan artifacts, or where the presence of a metal monitor is contraindicated (e.g., MRI scans). Therefore, we believe there is only a minimal increase in risks from participating in the study. This risk relates to the possibility of developing irritation to the skin at the site of placement.

	
Subjects will be monitored for Adverse Events, Serious Adverse Events, and Device-Related Adverse Events from BIS™ sensor applications throughout the BIS™ sensor removal.

Statistics	
Standard demographic information and baseline characteristics will be summarized using descriptive statistics. For safety assessments, adverse events (AEs) will be summarized using frequency counts and percentages. Descriptive statistics will be provided by severity and relationship as needed.
 
The primary analysis will be based on all evaluable data (excluding training subjects). Normality of data will be tested using the Kolmogorov-Smirnov test. Depending on whether normality assumption hold, a two group t-test or Wilcoxon rank-sum test will be used to compare between the two treatment groups. A P-value of less than 0.05 is considered statistically significant unless otherwise specified.
 
The secondary endpoints will be evaluated using the Holm-Bonferroni method to ensure the overall type I error rate is controlled at the 0.05 level.
 
Cardiovascular Variables will be summarized for both groups. The incidence of hypotension will be summarized and compared to anesthesia sedation levels.
 
The anesthetic requirements with the BIS™ value, the percentage of time during maintenance with BIS™ values within the specified ranges, and number of episodes and duration of burst suppression will be assessed for both treatment groups.
 
Additional endpoints, including PAED scale, Pain Rating Score and a subgroup analysis for subjects requiring neuromuscular blockade, will be summarized using descriptive statistics for each group and groups combined.

4. Introduction

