10.9.3.3 BIS™ Guided Group

In the BIS™ group, sevoflurane will be adjusted to achieve a target BIS™ values of 45 – 60 during maintenance of anesthesia and BIS™ values of 60 – 75 beginning of skin closure. Subjects with BIS™ values that are outside of the specified range of 45 – 60 during maintenance of anesthesia for >35% of the maintenance duration will be considered a protocol deviation and the subject will be excluded from the final data analysis and will be replaced by an additional subject. The excluded subject will continue to be monitored for any safety events and the clinical will ensure that medical care is provided should a safety event occur. Data from the excluded subject will be acknowledged in the final study report but will not be

included in the primary statistical analysis. The exception to this exclusion is any data that is outside of the specified range of 45 – 60 as a result of the anesthesiologist titrating medications as a result of clinical signs or cardiovascular changes defined above. Additionally, data points will be excluded if significant artifact is present or if the sevoflurane concentration or BIS™ value is missing.

At the completion of the surgery, and after confirmation of the return of neuromuscular function, sevoflurane will be discontinued, and discontinuation time will be recorded, and as applicable, extubation will be performed when the patients demonstrate the purposeful movement, facial grimace, or eye-opening to jaw thrust.

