13.1 Clinical Events Committee Review

This study will have the Steering Committee. The Steering Committee is composed of physicians with expertise in the area of Anesthesiology monitoring in pediatric patients, who will assume a leadership role in the overall study. The Steering Committee's roles are to:

- Develop the protocol along with Medtronic, to ensure its scientific and statistical soundness;
- Review the conduct of the study;
- Help identify and resolve problems with recruitment or performance

This study is considered a non-significant risk for study participants. Thus, the need for additional safety oversight beyond Medtronic's already rigorous safety monitoring processes is not required. A Medtronic Medical Advisor, as needed, will provide an independent medical review according to the study Safety and Complaint Management Plan. The Medical Advisor will not be affiliated with an investigative center.

14. Statistical Design and Methods

Statistical analyses will be conducted by Medtronic or its designee as outlined in the Statistical Analysis Plan (SAP.) Any changes in statistical methods will be detailed in the Clinical Study Report. Data exclusion will be captured in the Data Management Plan.

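### The protocol says that no treatment decisions are made and that the sensor is the only change in care, but the BIS arm's sevoflurane is titrated to a protocol target, and the risk section omits the depth-of-anesthesia risk that the synopsis acknowledges

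*Protocol*

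**What the plan says.** **Statements that care is unchanged.** Section 11.1 says: "No treatment or treatment decisions will be made during the course of this study". The synopsis, under Safety Assessments, calls this a randomized study in which "the only change in routine management is the placement of the BIS™ monitor probe on the forehead". Section 10.9.7 says that the choice, dose and route of sedative drugs "will not be changed for the purposes of the study". After a sentence on where the monitor will not be used, it continues: "Therefore, we believe there is only a minimal increase in risks from participating in the study". It then describes that risk: "This risk relates to the possibility of developing irritation to the skin at the site of sensor placement".

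**Statements that care is changed.** The synopsis (Study Design) says that in the BIS group "sevoflurane will be titrated to achieve a target BIS™ value of 45 – 60 during maintenance of anesthesia", with a second, higher target from the start of skin closure. Section 10.9.3.3 repeats that "sevoflurane will be adjusted to achieve a target BIS™ values of 45 – 60 during maintenance of anesthesia", and SAP section 5 says the same. For specified hemodynamic or clinical signs, the synopsis lists drug or fluid steps that come before the anesthesiologist may leave the BIS range. A BIS-arm child outside 45–60 for more than 35% of maintenance is a protocol deviation, excluded and replaced, unless the excursion came from titration to clinical signs. (SAP section 7.4, written against an earlier protocol version, gives 25%.)

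**Risk and oversight.** Sections 11.3 and 11.4 determine that the study is of non-significant risk (NSR), citing the nature of the devices and four FDA criteria. Section 13.1 says "This study is considered a non-significant risk for study participants" and concludes that no additional safety oversight is needed.

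**The concern.** A trial that randomizes children to two ways of setting the anesthetic does make treatment decisions by protocol in one arm. If the risk text describes only a sensor on the forehead, the IRB is asked to accept a minimal-risk argument for something narrower than what is delivered. The harm that guided titration could plausibly cause is anesthesia that is too light or too deep, and the section meant to set out the study's risks does not mention it. The safety plan then has no stated place for that harm: there is no instruction on classifying events that arise from titration, and the SAP names no analysis for movement, grimacing, eye opening and the other clinical signs that would show it.

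**Working it through.** The check is mainly textual; the arithmetic only sizes it.

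**1. The passages side by side**

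| Topic | Risk text | Procedure text |
|---|---|---|
| Treatment decisions | None made (11.1) | Sevoflurane titrated to a BIS target in one arm (Synopsis, Study Design; 10.9.3.3; SAP 5) |
| Change in routine care | Probe placement only (Synopsis, Safety Assessments) | Target ranges, ordered steps before leaving the range, exclusion if off target too long (Synopsis; 10.9.3.3) |
| Drug choice and dose | Not changed for the study (Synopsis; 10.9.7) | Sevoflurane differs by randomized arm, by design |

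The risk text is stated for the whole study, with no exception for the BIS arm. A reader could take the sedative-drug sentence in 10.9.7 to mean premedication only. That would not rescue the other two statements, and it would leave the minimal-risk inference silent on sevoflurane.

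**2. Does the protocol recognize the missing risk?** Yes. The synopsis (Study Design) requires assessment about every 5 minutes specifically to guard against inadequate or excessive anesthesia in the BIS-guided group. Section 4.1.2 says that light anesthesia can lead to awareness with recall and that overly deep anesthesia can cause hemodynamic and respiratory problems. In section 11, 11.1.1 covers sensor contact, 11.1.2 refers to the instructions for use, 11.1.3 covers oximetry sensors, and 11.1.4 lists general anesthetic side effects. None names inadequate or excessive depth or links a risk to BIS-guided titration.

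**3. Does the design expect the arms to differ?** Inputs from section 14.2: 18 per arm in each age group, difference 0.5%, SD 0.5%, two-sided alpha 0.05, stated power above 80%.

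- Normal approximation: 0.5 / (0.5 × √(2/18)) = 3.00, and power = Φ(3.00 − 1.96) = 85.1%.
- Two-sample t-test: 83.0%.
- For 80% power: 16 per arm (normal) or 17 (t-test).

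The stated figure reproduces. The trial is powered to detect a between-arm difference in anesthetic concentration, which could not arise from the intervention if the sensor were the only change.

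**4. Size of the exposure**

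- Children affected: 3 age groups × 18 = 54 of 108, as a minimum.
- Prior study, ages 3–18 (section 4.1.3.2, Table 2): maintenance sevoflurane 2.4% under standard practice and 1.8% under BIS guidance, so (2.4 − 1.8)/2.4 = 25% lower. A 0.5-point fall from 2.4% would be 0.5/2.4 = 20.8%.
- In the same group, mean maintenance BIS under standard practice was 39.6, below this trial's lower limit of 45.

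These percentages are illustrative. The prior study used 60% nitrous oxide throughout; here nitrous oxide stops after airway placement (10.9.2). They describe exposure to the agent, not harm.

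**5. What depends on the incorrect text?** The minimal-risk conclusion in the synopsis and 10.9.7 is drawn directly from it. The NSR determination in 11.3 is not: it gives device-based reasons and does not cite the sentence in 11.1. It also does not discuss BIS-guided titration, and section 13.1 draws its oversight decision from it.

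**The case against.** The strongest reply is that the contradiction is one of wording and that most consequences a reader might infer from it are not supported. Much of this stands.

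- **A reader might infer that the NSR determination is invalid.** The documents do not show that. Section 11.3 rests on the nature of the devices. Those devices are market-released (7.1), used within cleared indications (7.3), and indicated for use with sevoflurane in pediatrics (7.4.1). The determination is incomplete on guided titration, not refuted.
- **A reader might infer that light-anesthesia events will be coded as not device-related.** The definition in section 12.1 covers events from the device's presence or performance, intended or otherwise, so harm from BIS-guided titration already fits. Investigator and sponsor both classify relatedness (12.2.1). What remains is that neither has an instruction for such events, so coding may be inconsistent.
- **A reader might infer that IRBs and parents are told of a different intervention.** IRBs approve the protocol itself (8.2), which describes the titration. The consent form is not in the available documents, so its content cannot be judged.
- **A reader might infer that the events would go unseen.** Section 12.3.2 captures hypotension, hypertension, movement, grimacing, eye opening, tearing and sweating. SAP 7.10 summarizes adverse events for each study group, and SAP 7.9 summarizes cardiovascular variables for both arms. The gap is narrower: the Clinical Anesthesia Assessment is a listed endpoint with no named analysis, and no between-arm estimate is planned.
- **A reader might infer that the sample size assumes less sevoflurane in the BIS arm.** Section 14.2 gives a two-sided detectable difference. The expectation of a reduction comes from the background and section 6.2.
- **A reader might say that the protocol fixes the dose.** It sets a BIS target, and the clinician may override it.

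The reply does not remove the contradiction or the omission from section 11.

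**Conclusion.** The point holds as an internal contradiction with a safety consequence. Section 11.1, the synopsis (Safety Assessments) and section 10.9.7 cannot stand together with the synopsis (Study Design), section 10.9.3.3 and SAP section 5. The minimal-risk reasoning misdescribes the BIS arm, which is at least 54 of 108 analyzed children, and section 11 omits a risk that the protocol acknowledges elsewhere. The NSR rationale does not address guided titration, yet it is the ground for declining further oversight. It would go too far to say that the NSR conclusion or the relatedness coding rests on a false premise, for the reasons above. The primary estimate, the power and the sample size are unchanged. The verdict rests on the text as released; the consent form was not available. It should be corrected, because the statements are wrong as written and the correction is cheap.

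**What to change.** 1. Reconcile section 11.1, the synopsis (Safety Assessments) and section 10.9.7 with the synopsis (Study Design and Maintenance), section 10.9.3.3 and SAP section 5, so that all say the same about how sevoflurane is managed in each arm.
2. Carry the risk of inadequate or excessive anesthesia, already acknowledged in the synopsis, into section 11, and check that the consent form matches.
3. Restate the minimal-risk and NSR rationale to IRBs so that it addresses BIS-guided titration, and confirm the oversight decision in section 13.1 on that basis.
4. In section 12.2.1, state one rule for classifying events that may arise from anesthetic titration, applied identically in both arms. Presuming device-relatedness in the BIS arm alone would code the same event differently by arm and bias the relatedness table.
5. In SAP 7.10, report the Clinical Anesthesia Assessment and the section 12.3.2 events by arm, regardless of attribution, with risk differences and 95% confidence intervals.

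The cost is a protocol text amendment with IRB notification, any consent change that follows, and one extra table from data already collected. No view is taken on BIS targets, doses or clinical rules.
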